5.2 Safety assessments

5.2.1 Laboratory safety assessments

Blood and urine samples for determination of clinical chemistry, haematology, and urinalysis will be taken at the times indicated in the Study Plan (see Section 4). Additional safety samples may be collected for analysis at local laboratory, if clinically indicated at the discretion of the investigator.

The detailed methods for specimen collection, handling, processing, shipping, and storage will be supplied in the Investigator's Laboratory Manual provided by the Central Laboratory.

The following laboratory variables will be measured:

Table 3 Laboratory Safety Variables

Haematology/Haemostasis (whole blood)	Clinical Chemistry [serum (S) or plasma (P)]
B-Haemoglobin (Hb)	S-Aspartate transaminase (AST)
B-Hematocrit	S-Alanine transaminase (ALT)
B-Red blood cell count	S-Alkaline phosphatase (ALK-P)
B-White blood cell count	S-Bilirubin, total
B-Platelet count	S-Blood Urea Nitrogen
	S-Creatinine
Urine analysis (dipstick)	S-Albumin
Blood (Microscopy if dipstick positive for blood)	S-Total protein
Pregnancy test (Urine HCG pregnancy test for WOCBP (HCG minimum sensitivity of 25 IU/L), dipstick analyzed at the study centre)	CCI
	S-Potassium
Urine analysis (spot urine)	S-Calcium, total
Creatinine	S-Sodium
Albumin	S- Bicarbonate
CCI	S- Chloride
Glucose (The quantitative urinary glucose values must not be disclosed during the double-blind phase (i.e., Visit 4 to 8) to maintain the blindness.)	S- Magnesium
	S- Phosphorus
	P- Parathyroid Hormone (PTH)
	S- 25-hydroxy-vitamin D
	S- β HCG, if urine pregnancy test result is positive
	Hepatitis Screen Panel (Includes Hepatitis B viral antibody IgM, Hepatitis B surface antigen and Hepatitis C virus antibody).

The Investigator should make an assessment of the available results with regard to clinically relevant abnormalities. The laboratory results should be signed and dated and retained at centre as source data for laboratory variables. For information on how AEs based on laboratory tests should be recorded and reported, see Section 6.3.

NB. In case a patient shows an AST and/or ALT $\geq 3 \times \text{ULN}$ and TB $\geq 2 \times \text{ULN}$, please refer to [Appendix C](#) “Algorithm on Management of Sustained Elevated Liver Safety Abnormalities”, for further instructions.

5.2.2 Physical examination

A brief physical examination should include the CV system, lungs, abdomen, and extremities, and any organ system pertinent to the patient’s signs, symptoms, or AEs. The patient should always be evaluated for the presence of oedema. A complete physical examination should include general appearance, head, eyes, ears, nose, throat, neck, CV system, lungs, abdomen, lymph nodes, extremities, neurological system, skin, and musculoskeletal system. The patient should always be evaluated for the presence of oedema.

5.2.3 ECG

A 12-lead ECG will be taken after the patient has been lying down resting for at least 5 minutes. The ECG will be evaluated by the investigator and entered as ‘Normal’ or ‘Abnormal’ in the eCRF. If the ECG is evaluated as “Abnormal” the investigator should document the specific abnormality.

5.2.4 Vital signs

5.2.4.1 Blood pressure and pulse

As BP is both efficacy and safety variable in this study, measurement of seated BP is described in Sections [5.1.5](#).

Orthostatic BP: At selected visits where orthostatic BP and pulse are collected, supine and standing measurements should be made after the seated BP and pulse measurements have been made, using the same arm that was used for the seated BP measurements. All readings should be recorded in eCRF. Ideally, BP should be measured with the same equipment, at the same time of day, and by the same personnel at each visit.

The supine BP and pulse must be measured prior to the standing BP and pulse. After the patient rests in the supine position for at least 5 minutes, supine BP and pulse will be determined from three replicate measurements obtained at least 1 minute apart. All three readings must be recorded in eCRF. For study analyses, the average of the three BP and pulse readings will be used.

After the supine BP and pulse measurements are obtained, the patient will stand for 2 to 3 minutes. After this time, the BP will be measured with the arm supported at the level of the heart. Standing BP and pulse will be determined from three replicate measurements obtained at least 1 minute apart. All 3 readings must be recorded in eCRF. For study analyses, the average of the three BP and pulse readings will be used.

5.2.5 Other safety assessments

5.2.5.1 Self-monitored blood glucose and hypoglycemic events

The patients will be asked to check their blood glucose when they develop symptoms suggestive of hypoglycemia and to record specific symptoms in a hypoglycemia/blood glucose diary. Any results collected in the diary will be reviewed by the investigator at each visit. The investigator is responsible for questioning the patient about all symptoms reported in the diary and for determining if they meet the clinical definition of hypoglycemia. Only symptoms and/or blood glucose values that meet the definition of hypoglycemia should be reported on the hypoglycemia eCRF pages see Section 6.3.7. Glucometers will be provided by AstraZeneca.

Patients will be instructed to contact the investigator anytime they experience a hypoglycemic event. Hypoglycemic events must be recorded in the diary anytime a patient experiences either of the following:

- Signs and symptoms of hypoglycemia (regardless of blood glucose value by finger stick)
- Blood glucose value by finger stick <63 mg/dL (3.5 mmol/L) (regardless of symptoms).

Data to be collected for each hypoglycemic event:

- Date and time of episode (start and stop)
- Whether symptoms were present, and list of symptoms
- Possible contributing factors
- Whether a finger stick value was obtained, and if so, the blood glucose value
- Whether intervention was needed for recovery
- How the episode was treated
- Whether recovery was prompt after treatment
- Time of last anti-diabetic agents administration
- Time of last meal and its contents

The patient diary will be reviewed and added to the patient's source record. A new diary for the next period will be handed over to the patient if needed

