6.3.7 Hypoglycemic events

A separate section in the eCRF will be used to document all reported episodes of hypoglycaemia (see Section [5.2.5.1](#)). Hypoglycemic episodes should also be reported on the AE eCRF page if the event fulfils protocol criteria for a SAE (see Section [6.2](#)).

- Major hypoglycemic events, defined as symptomatic events requiring external assistance due to severe impairment in consciousness or behaviour, with a capillary or plasma glucose value <54 mg/dL (<3.0 mmol/L), and prompt recovery after glucose or glucagon administration.
- Minor hypoglycemic event, defined as either a symptomatic episode with a capillary or plasma glucose measurement <63 mg/dL (<3.5 mmol/L) regardless of need for external assistance or an asymptomatic capillary or plasma glucose measurement below 63 mg/dL (3.5 mmol/L), that does not qualify as a major episode.

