##### **4.2.7.1.6.1 Hypoglycemia**

Separate pages to capture events of hypoglycemia are contained within the CRF.

Hypoglycemic events with an onset from Day 1 of the double-blind treatment period up to and including 4 days (30 days for SAE) after the last dose date in the double-blind treatment period will be considered as occurring during the double-blind treatment period. The

proportion of patients with hypoglycemic events will be tabulated by treatment group in the double-blind treatment period. Both primary and sensitivity safety analyses will be performed. Hypoglycemic events will be categorized using the following classes:

- Major episodes of hypoglycemia - defined as symptomatic episodes requiring external (3rd party) assistance due to severe impairment in consciousness or behaviour, with a capillary or plasma glucose value  $<3$  mmol/L ( $<54$  mg/dL), and prompt recovery after glucose or glucagon administration,
- Minor episodes of hypoglycemia - defined as either a symptomatic episode with a capillary or plasma glucose measurement below 3.5 mmol/L (63 mg/dL) regardless of need for external assistance, or an asymptomatic capillary or plasma glucose measurement below 3.5 mmol/L (63 mg/dL), that does not qualify as a major episode,
- Other episodes of hypoglycemia - defined as episodes reported by the investigator that are suggestive of hypoglycemia but do not meet the above criteria.

When summarizing hypoglycemic events leading to discontinuation no upper cutoff day windows are applied.

A listing of patients will be produced and it will display all hypoglycemic events with an onset on or after the start date of double-blind treatment period.

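### Protocol 5.2.5.1 conflicts with Protocol 6.3.7 and SAP 4.2.7.1.6.1 on which hypoglycaemia episodes enter the eCRF, so the 'Other' row and the any-hypoglycaemia proportion may be under-ascertained or unevenly ascertained across sites

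*Protocol*

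**What the plan says.** **Diary.** Under Protocol 5.2.5.1 patients record an event for a finger-stick value below 63 mg/dL with or without symptoms, and also for symptoms whatever the reading: "Signs and symptoms of hypoglycemia (regardless of blood glucose value by finger stick").

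**From diary to eCRF.** The investigator reviews the diary symptoms and is responsible "for determining if they meet the clinical definition of hypoglycemia". The entry rule follows: "Only symptoms and/or blood glucose values that meet the definition of hypoglycemia should be reported on the hypoglycemia eCRF pages see Section 6.3.7". The list of data to collect for each event in the same section includes "Whether a finger stick value was obtained, and if so, the blood glucose value".

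**Protocol 6.3.7.** The section begins: "A separate section in the eCRF will be used to document all reported episodes of hypoglycaemia". It then defines two classes. A major event needs external assistance "with a capillary or plasma glucose value <54 mg/dL (<3.0 mmol/L), and prompt recovery after glucose or glucagon administration". A minor event is either "a symptomatic episode with a capillary or plasma glucose measurement <63 mg/dL (<3.5 mmol/L) regardless of need for external assistance" or an asymptomatic reading below the same threshold. An episode also goes on the AE page if it meets the SAE criteria.

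**SAP.** Section 4.2.7.1 takes the separate hypoglycaemia summaries from the hypoglycaemia CRF pages. Section 4.2.7.1.6.1 tabulates the proportion of patients with hypoglycaemic events by treatment group. It classes events as major, minor, or a third category: "Other episodes of hypoglycemia - defined as episodes reported by the investigator that are suggestive of hypoglycemia but do not meet the above criteria". The protocol does not mention this third class.

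**The concern.** The entry rule points to a section in which every defined class needs a glucose reading. Taken literally, it keeps off the eCRF exactly the episodes that the SAP later counts as 'Other'. The SAP cannot repair this, because it classifies only what was entered.

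The opening sentence of 6.3.7 gives the opposite instruction, so two sites could handle the same episode differently in good faith. With 302 patients planned at about 100 centres (302/100, or about 3 per centre), the pooled proportion could mix two ascertainment rules, and the database would not show which rule a site used.

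The study includes insulin and sulfonylurea strata, and the SAP gives hypoglycaemia its own tables. A non-serious episode has no second route into those tables: the AE page takes hypoglycaemia only when it is an SAE, and SAP 4.2.7.1 says the same of discontinuation for hypoglycaemia. The clearest case is a non-serious episode in which someone helped the patient before a reading was taken. It is neither major nor minor, so it is counted as hypoglycaemia only if it is entered and classed as 'Other'.

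**Working it through.** The documents state no hypoglycaemia rate, so there is no planned figure to reproduce. The check has two parts.

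**1. Follow each kind of episode through both rules.** 'Strict' means 5.2.5.1 with its cross-reference taken literally. 'Open' means the first sentence of 6.3.7.

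| Episode | Class in 6.3.7 | Strict | Open | SAP class |
|---|---|---|---|---|
| Meets the full major definition (reading <54 mg/dL) | major | entered | entered | major |
| Other episode with a reading <63 mg/dL, with or without symptoms | minor | entered | entered | minor |
| Symptoms, reading ≥63 mg/dL | none | not entered | entered | Other |
| Symptoms, no reading | none | not entered | entered | Other |
| Assisted, no reading, not an SAE | none | not entered | entered | Other |

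The thresholds agree between the documents (54 mg/dL with 3.0 mmol/L; 63 mg/dL with 3.5 mmol/L), so the first two rows are the same under both rules. Episodes that meet the SAE criteria also reach the AE page. The exposure is confined to the last three rows: the 'Other' category and any total that includes it.

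**2. Illustrate the possible size.** All three inputs are assumptions:

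- p = true proportion of patients with any episode
- s = share of those patients whose only episodes are non-qualifying
- c = fraction of those patients captured on the eCRF

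Reported proportion = p × [1 − s × (1 − c)], so loss = p × s × (1 − c).

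| p | s | Reported, c = 0 | Reported, c = 0.5 | Reported, c = 1 |
|---|---|---|---|---|
| 20% | 10% | 18% | 19% | 20% |
| 20% | 20% | 16% | 18% | 20% |
| 30% | 10% | 27% | 28.5% | 30% |
| 30% | 20% | 24% | 27% | 30% |
| 30% | 30% | 21% | 25.5% | 30% |

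For the last row at c = 0: 0.30 × (1 − 0.30) = 0.21, a loss of 9 percentage points. At c = 0.5 the loss is 0.30 × 0.30 × 0.5 = 0.045, or 4.5 points. At c = 1 it is zero. In relative terms the loss runs from 0 to s, and the documents do not fix where it falls.

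**Between arms.** If s and c are the same in both arms, each proportion is multiplied by the same factor. A true 30% versus 20% at s = 30% and c = 0 is reported as 21% versus 14%. The ratio stays at 1.5; the absolute difference shrinks from 10 to 7 points.

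**The case against.** The best defence is that the protocol, read as a whole, intends the open rule. The investigator applies a clinical judgement to diary symptoms, the entry sentence admits symptoms and/or values, the data list allows for an event with no reading, and 6.3.7 speaks of all reported episodes. On that reading the investigator screens out what is not hypoglycaemia, enters the rest, and the SAP sorts it; 'Other' fits naturally. Protocol section 5 also says that completion instructions accompany the CRF. They are not among the documents and may settle the matter.

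Much of this stands. It rules out three stronger conclusions that a reader might draw:

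- **That the protocol bars symptom-only episodes and reported incidence is therefore too low.** That follows only where sites take the strict reading, and the loss starts at zero.
- **That a filtered-out episode disappears altogether.** Protocol 6.3.5 requires reported or observed AEs to be recorded, so symptoms not judged to be hypoglycaemia could appear as symptom AEs, though not as hypoglycaemia.
- **That the comparison between arms is distorted.** Nothing suggests that recording habits differ by arm in a double-blind, centrally randomised study, and equal loss preserves the ratio. The shrinkage of the absolute difference in the example rests entirely on assumed inputs. Protocol 8.5.7 also keeps the safety analysis descriptive, without inferential testing.

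What the defence does not remove is the conflict itself. The clinical definition is never stated separately, the only definitions at the cross-reference need a reading, and the class that the SAP counts is absent from the protocol. A site that obeys the entry sentence and its cross-reference is not misreading the plan.

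**Conclusion.** The point holds as an internal inconsistency with a limited consequence. Protocol 5.2.5.1 and the opening of 6.3.7 give incompatible entry rules, and the SAP tabulates a class that the protocol does not define and that one of those rules would leave empty. The 'Other' row and the any-hypoglycaemia proportion may be under-ascertained, or ascertained differently from site to site. Major, minor and SAE episodes are unaffected.

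The size cannot be derived from the documents. Under the assumed 30% of patients with any episode and 30% of those with only non-qualifying ones, it is 0 to 9 percentage points; the upper end requires every site to apply the strict reading. Whether sites actually diverged cannot be known from the plan. It is still worth correcting, because the listed data items already cover what is needed and the remedy is mainly one of wording.

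**What to change.** Reconcile the three places:

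1. Reword the entry sentence in Protocol 5.2.5.1, and any matching eCRF completion instruction, so that every diary episode the investigator judges to be hypoglycaemia is entered, whether or not it meets the major or minor definition.
2. Add the 'Other' class to Protocol 6.3.7, matching SAP 4.2.7.1.6.1.
3. Assign major, minor or other from the recorded fields (symptoms, reading if any, intervention, recovery).

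If this comes too late for data already collected, present major and minor as the consistently ascertained categories. Show 'Other' and the any-event total separately, with a note on how episodes were ascertained. Querying sites before Clean File for diary episodes that were not transcribed is optional; the diary is part of the source record, but the work would extend across about 100 centres.

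**Cost.** The rewording needs a protocol amendment or a site instruction, with ethics review where Protocol 10.5 requires it. Some non-specific symptomatic episodes will enter the total, but they remain visible in the 'Other' row. Investigator judgement about what counts as hypoglycaemia remains, so variation between sites is reduced rather than eliminated. The change concerns recording only.

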5.2.5.2 Hepatic events (Hepatic Adjudication Committee)

An independent Hepatic Adjudication Committee, blinded to the treatment of the patients, will determine the probability that drug-induced liver injury (DILI) is the cause of liver-related abnormalities, including, but not limited to:

- Hepatic events timely related to death (within 30 days before death)
- AST and/or ALT >3x ULN and TB >2x ULN (within 14 days of the AST and/or ALT elevation)
- AST and/or ALT >10x ULN

A separate Adjudication Manual will define and describe the procedure for the handling, reporting and classification of these cases.

5.2.5.3 Asymptomatic bacteriuria

The following is presented to assist in the classification and management of asymptomatic bacteriuria in studies with dapagliflozin. It is not intended to supplant investigators' clinical judgement.

During enrolment, treatment and follow up of patients in this study, the investigator may discover a patient with asymptomatic bacteriuria. Asymptomatic bacteriuria is defined as the presence of $\geq 10^5$ colony forming units/mL of bacteria, in a properly collected voided urine specimen, without signs or symptoms typically attributed to urinary tract infection (UTI). Asymptomatic bacteriuria is prevalent among diabetic women, and is associated with pyuria in 70% of cases. Neither guidelines from the US (Nicolle et al 2005, USPSTF 2008) nor Europe (EAU 2014) recommend screening for, or treatment of, asymptomatic bacteriuria in non-pregnant diabetic patients. In this study, the central laboratory will report urinary dipstick test results for hemoglobin but will not routinely report the results of urinary dipstick tests for leukocyte esterase as a screening test for pyuria in surveillance urine examinations.

5.2.5.4 Microscopic Hematuria

In the event that hematuria is observed during a patient's participation, the sponsors recommend standard of care in diagnosing the cause of the hematuria. This section presents references and an example of standard of care evaluation of microscopic hematuria. Local standards of care should be followed.

Patients with repeated reports of microscopic hematuria in 2 or more properly collected urine samples need to have follow-up for this result according to standard of care. The American Urological Association defines microscopic hematuria as three or more red blood cells per high-power microscopic field in urinary sediment from two or more properly collected urinalysis specimens (AUA, Grossfeld et al 2001). These Best Practice guidelines have been evaluated by Jung in a study of 772000 patients (Jung et al 2011).

Patients who show microscopic hematuria that is accompanied by significant proteinuria, red blood cell casts, or dysmorphic red blood cells in the sediment should be evaluated for the presence of primary renal disease and need to be referred to a nephrologist (AUA, Grossfeld et al 2001).

Patients who lack other explanation for their hematuria, or who have risk factors for significant urologic disease, will need a urological evaluation and should be referred to an urologist. Risk factors for significant urological disease include unexplained microscopic hematuria as well as smoking history, occupational exposure to dyes or chemicals (such as benzenes or aromatic amines), visible hematuria, age >40 years, previous urologic history, history of irritative voiding symptoms, history of UTI, analgesics or phenacetin abuse, history of pelvic irradiation, or cyclophosphamide use (AUA, Greenwood M 1926). Results from any procedure or investigations should be reported on the eCRF.

5.2.5.5 Volume Depletion

The risk of electrolyte abnormalities, volume depletion, and impaired renal function is enhanced when two diuretics are used in combination. For this reason, caution should be exercised when administering dapagliflozin, which has a modest diuretic effect, to patients who are taking loop diuretics. These patients should have careful monitoring of electrolytes, volume status, and renal function. Loop diuretic dose adjustments should be made if clinically indicated.

5.2.5.6 Potential events of Diabetic Ketoacidosis

All potential events of DKA will be recorded in the eCRF and submitted to an independent DKA Adjudication Committee. The DKA Committee T2DM will assess available information on each potential DKA event and will classify the event in accordance with the definitions in the DKA Adjudication Charter T2DM.

The DKA Adjudication Committee will be kept blinded to the study drug treatment received by each patient with a potential DKA event in the clinical study. A separate DKA Adjudication Manual will define and describe the procedures for the collection of DKA information, handling, adjudication criteria and reporting of these events/cases.

5.3 Other assessments – Not Applicable

5.4 Pharmacokinetics – Not Applicable

5.5 Pharmacodynamics – Not Applicable

5.6 Pharmacogenetics – Not Applicable

5.7 Biomarker analysis – Not Applicable

5.8 Storage, re-use and destruction of biological samples

After the analyses are complete the samples will be either completely consumed during the analytical process or disposed of after the analysis.

5.9 Labelling and shipment of biological samples

The Principal Investigator (PI) ensures that samples are labelled and shipped in accordance with the Laboratory Manual and the Biological Substance, Category B Regulations (materials containing or suspected to contain infectious substances that do not meet Category A criteria), see [Appendix B](#) 'IATA 6.2 Guidance Document'.

Any samples identified as Infectious Category A materials are not shipped and no further samples will be taken from the patient unless agreed with AstraZeneca and appropriate labelling, shipment and containment provisions are approved.

